11.3. Quality Assurance

By signing this protocol, the Sponsor and Investigator agree to be responsible for implementing and maintaining quality control and quality assurance systems with written standard operating procedures (SOPs) to ensure that studies are conducted and data are generated, documented, and reported in compliance with the protocol, accepted standards of GCP, and all applicable federal, state, and local laws, rules and regulations relating to the conduct of the clinical study.

11.3.1. Development of Monitoring Plan

Onsite monitoring visits will be conducted by DCC monitors according to a pre-defined Monitoring Plan. The monitoring plan will detail the frequency of on-site visits, the study data to be monitored, the review of any regulatory files, drug and supplies accountability (if applicable), documentation of the on-site visit, and the resolution process for data errors that are discovered during the visits.

NN108 Topiramate as a Disease Modifying Therapy for CSPN

Version 8.0

Version date 8/8/2018

All participating clinical study sites will be monitored at least once after a study initiation visit and all sites will have a close-out visit for each protocol. One on-site monitoring visit is anticipated for each clinical study site per year. All subjects will be monitored for inclusion and exclusion criteria, informed consent procedures, and adverse events. A certain percentage of data is also monitored/ source data verified against the data entered into the study database. The monitoring plan will include flexibility to revise the frequency of visits or data monitored depending on clinical study site or study related issues.

11.3.2. Site Monitoring Visits

On-site monitoring visits will be conducted by DCC monitors according to a pre-defined monitoring plan for each protocol. The goal of on-site monitoring is to analyze (review) the data as it is collected, to check the validity and integrity of the data, to verify source documentation, to ensure protection of human subjects, and to ensure protocol compliance with federal regulations. During the monitoring visit, the monitor assesses the overall status of the study, staff, and facilities to determine whether the study is being conducted per protocol and in compliance with regulatory requirements. The monitor also conducts a CRF review that includes checks of all adverse event documentation, verifies the presence of all critical correspondence and records related to investigational products and clinical supplies (if applicable), and determines if protocol violations have occurred and are documented properly. After the monitoring visit, the monitor documents the results of the monitoring visit and completes a post-visit monitoring letter that conveys any issues discovered during the visit and the need for data corrections, if appropriate. Drug and supplies accountability may also be monitored during the site visit. The DCC will work closely with the CCC to monitor and document drug distribution from the manufacturers to the clinical study sites (CSS). Each CSS will be provided with a drug accountability log which will be reviewed by the DCC monitors and reconciled with distribution logs. At the study closeout visit, the monitors confirm that appropriate data have been reviewed, source documentation has been verified, and all required documents are present in the Study Regulatory File.

11.3.3. Laboratory Data Flow

Safety Monitoring Labs: The DCC will provide laboratories with online forms and/or electronic data exchange mechanisms - depending on their capabilities and needs - to enter, update and obtain relevant data. When a blood or urine sample has been obtained, the clinical study site study coordinator will send the sample (subject ID, site ID, and protocol ID numbers will be used) to the University of Rochester central laboratory. Results will be sent via a secure system to University of Rochester laboratory with no individual-identifying information on the report. The laboratory will electronically communicate the test results to the respective clinical study sites in a secure manner. The laboratory will also transfer test results electronically to the DCC.

11.4. Adverse Experience Reporting

The adverse event (AE) definitions and reporting procedures provided in this protocol comply with all applicable United States Food and Drug Administration (FDA) regulations and International Conference on Harmonization (ICH) guidelines. The Site Investigator will carefully monitor each

subject throughout the study for possible adverse events. All AEs will be documented on CRFs designed specifically for this purpose. It is important to report all AEs, especially those that result in permanent discontinuation of the investigational product being studied, whether serious or non-serious.

Each clinical study site's Principal Investigator and research team are responsible for identifying adverse events and reporting them through the DCC Online Adverse Event Reporting System. Investigators are also responsible for complying with NeuroNEXT CIRB's reporting requirements for all safety reports. Copies of each report and documentation of IRB notification and receipt will be kept in the investigator's study file.

An adverse event is defined as: "...an unfavorable and unintended sign, symptom, or disease associated with a subject's participation in this research trial."

Serious adverse events include those events that: "result in death; are life-threatening; require inpatient hospitalization or prolongation of existing hospitalization; create persistent or significant disability/incapacity, or a congenital anomaly/birth defects."

Unexpected adverse event is defined as any adverse experience...the specificity or severity of which is not consistent with the risks described in the protocol.

Expected adverse events are those that are known to be associated with or have the potential to arise as a consequence of participation in the study.

On-line Adverse Event Reporting System

Upon entry of a serious adverse event by a site investigator, the DCC Online Adverse Event Reporting System will immediately notify the Independent Medical Monitor (IMM).

Within **24 hours** (of learning of the event), investigators must report any Serious Adverse Event (SAE) Investigators must report all other AEs within **5 working days/7 calendar days** (of learning of the event).

Serious adverse events: The site investigator determines causality (definitely not related, probably not related, possibly related, probably related, definitely related) of the adverse event. The IMM will review the SAE report. The IMM may request further information if necessary. The Online Adverse Event Reporting System maintains audit trails and stores data (and data updated) and communication related to any adverse event in the study. The IMM may determine that the Serious Adverse Event requires expedited reporting to the FDA. The DCC will prepare a Medwatch safety report for submission to the FDA. If warranted, the IMM will notify the DSMB chair. The DSMB may suggest changes to the protocol or consent form to the Study Chair as a consequence of adverse events.

Non-serious adverse events: Non-serious adverse events that are reported to or observed by the investigator or a member of his research team will be submitted to the DCC in a timely fashion (within 5 working days). The events will be presented in tabular form and given to the IMM on a quarterly basis or as requested. Local site investigators are also required to fulfill all reporting requirements of their local institutions.

The DCC will prepare aggregate reports of all adverse events (serious/not serious, expected/unexpected and relationship to study drug) for the IMM and the DSMB on a quarterly basis or as requested. In addition, all adverse events will be coded using the MedDRA system. A separate report detailing protocol compliance will also be available from the DCC for DSMB and/or site review monthly or as requested. The research team will then evaluate whether the protocol or informed consent document requires revision based on the reports.

11.4.1. Definitions of Adverse Events, Suspected Adverse Drug Reactions & Serious Adverse Events

11.4.1.1. Adverse Event Collection and Reporting

Subjects will be monitored for AEs from the time they sign consent until 30 days following permanent discontinuation of study drug. Adverse events during the screening phase (from the time the subject signs consent until they are randomized) shall only include events related to study procedures, i.e. infection of skin biopsy site. If not related to study procedures, any new or worsened medical conditions reported during the screening process will be recorded in medical history.

An adverse event (AE) is any unfavorable and unintended sign (including a clinically significant abnormal laboratory finding, for example), symptom, or disease temporally associated with a study, use of a drug product or device whether or not considered related to the drug product or device.

Adverse drug reactions (ADR) are all noxious and unintended responses to a medicinal product related to any dose. The phrase “responses to a medicinal product” means that a causal relationship between a medicinal product and an adverse event is at least a reasonable possibility, i.e., the relationship cannot be ruled out. Therefore, a subset of AEs can be classified as suspected ADRs, if there is a causal relationship to the medicinal product.

Examples of adverse events include: new conditions, worsening of pre-existing conditions, clinically significant abnormal physical examination signs (i.e. skin rash, peripheral edema, etc), or clinically significant abnormal test results (i.e. lab values or vital signs), with the exception of outcome measure results, which are not being recorded as adverse events in this trial (they are being collected, but analyzed separately).

Stable chronic conditions (i.e., diabetes, arthritis) that are present prior to the start of the study and do not worsen during the trial are NOT considered adverse events. Chronic conditions that

occur more frequently (for intermittent conditions) or with greater severity, would be considered as worsened and therefore would be recorded as adverse events.

Adverse events are generally detected in two ways:

Clinical → symptoms reported by the subject or signs detected on examination.

Ancillary Tests → abnormalities of vital signs, laboratory tests, and other diagnostic procedures (other than the outcome measures: the results of which are not being captured as AEs).

If discernible at the time of completing the AE log, a specific disease or syndrome rather than individual associated signs and symptoms should be identified by the Site Investigator and recorded on the AE log. However, if an observed or reported sign, symptom, or clinically significant laboratory anomaly is not considered by the Site Investigator to be a component of a specific disease or syndrome, then it should be recorded as a separate AE on the AE log. Clinically significant laboratory abnormalities, such as those that require intervention, are those that are identified as such by the Site Investigator.

An unexpected adverse event is any adverse event, the specificity or severity of which is not consistent with the current Investigators Brochure or package insert or described in the protocol. An unexpected, suspected adverse drug reaction is any unexpected adverse event that, in the opinion of the Site Investigator or Sponsor, there is a reasonable possibility that the investigational product caused the event.

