4.3. Subject Withdrawal Criteria

A subject may discontinue study drug or withdraw from study participation at any time without bias for any of the following reasons:

Administrative

1. Withdrawal of consent by subject
2. Request of Study Sponsor or Principal Investigator
3. Request of primary care physician
4. Pregnancy (must stop study drug)

NN108 Topiramate as a Disease Modifying Therapy for CSPN

Version 8.0

Version date 8/8/2018

5. Subject deemed lost to follow up/failure to return
6. Early termination of study
7. Other

Adverse Event

1. Worsening of the disease under study
2. Worsening of pre-existing disease (other than disease under study)
3. Intercurrent illness
4. Death
5. Major/clinically significant alteration in laboratory values after beginning study drug
6. Prolonged QTc
7. Active suicidal Ideation based on the C-SSRS
8. Other adverse event

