6.16. Diabetes

Patients who meet ADA criteria for diabetes at screening will be excluded. Those who develop diabetes during the course of the study may continue in the study. However, in the event a participant is found to have diabetes on follow up metabolic testing, their primary care provider will be notified.

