8. MANAGEMENT OF ADVERSE EVENTS

Extensive data regarding safety and adverse events are available from clinical trials of topiramate for epilepsy and episodic migraine. The dose of topiramate to be used in the TopCSPN Study is similar to that used for episodic migraine (50-200mg daily). Adverse events observed in randomized trials for migraine will be summarized⁶⁵. Following this summary, potentially significant adverse events observed at higher doses will be listed.

When topiramate must be discontinued for participant safety, the dose can be stopped immediately or titrated down based on the clinical judgement of the site investigator.

Adverse Events Observed at 100 mg daily of topiramate:

- Anorexia. Loss of appetite is one of the mechanisms contributing to weight loss. Most commonly anorexia is mild. In subjects complaining of intolerable anorexia, the dose will be tapered to the maximal tolerated dose.
- Fatigue. Subjects complaining of intolerable fatigue will be asked to taper the dose to the maximum tolerated.
- Memory Problems. Topiramate may cause confusion, psychomotor slowing, poor concentration, or memory loss. These symptoms are more commonly observed with rapid dose escalation. Patients complaining of intolerable memory problems, or those observed to have cognitive dysfunction sufficiently significant to warrant dose modification in the opinion of the PI will taper their dose to that maximally tolerated.
- Nausea. Subjects complaining of intolerable nausea will be asked to taper the dose to the maximum tolerated.
- Paresthesias. Paresthesias are typically mild and uncommonly lead to discontinuation. In the setting of this study, paresthesias may also be related to the underlying disease (CSPN), or nerve regeneration. There are no data suggesting topiramate causes or worsens peripheral neuropathy. Subjects experiencing increased paresthesias will be encouraged to continue to participate unless the symptom is severe enough in the opinion of the PI to warrant dose reduction.

Potentially serious adverse events noted in the package insert include:

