10.1.2. Secondary Outcome(s)

Secondary outcome measures will include measures of neuropathy symptoms and signs, function and mobility, nerve conduction studies, and metabolic assessment.

i. Neuropathy symptoms:

1. **NTSS6**⁵³

3. **Brief Pain Inventory – Diabetic Neuropathy (BPI-DN)**⁵⁴

ii. Neuropathy signs:

1. **Utah Early Neuropathy Scale**⁴⁸

iii. Function and mobility

1. **6-minute walk test (6MWT)**⁵⁶

2. **Timed up and Go (TUG)**⁵⁸

3. ABC Scale.

iv. Nerve conduction studies including Sural sensory amplitude and distal latency/conduction velocity, and Peroneal motor amplitude, distal latency, conduction velocity between the knee and ankle as described above.

v. Metabolic assessment:

- Height, weight, BMI, waist circumference
- Fasting glucose and insulin with calculation of the “quantitative insulin sensitivity check index” (QUICKI)⁷³
- Hemoglobin A1c
- Fasting lipid panel

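### The exception that keeps outcome-measure results off the adverse-event log is not limited to efficacy measures, so as written it also bars clinically significant weight and metabolic results

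*Combined protocol and SAP*

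**What the plan says.** Section 11.4.1.1 (Adverse Event Collection and Reporting) takes in any untoward sign, symptom, disease or clinically significant laboratory finding. Its examples start with new conditions and end with clinically significant abnormal test results, and to that last item it attaches an exception: "with the exception of outcome measure results, which are not being recorded as adverse events in this trial". It adds that such results are still gathered and are analysed separately. The paragraph on how events are detected repeats the exception under ancillary tests: "other than the outcome measures: the results of which are not being captured as AEs".

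Section 10.1.2 includes metabolic assessment among the secondary outcome measures. The items are "Height, weight, BMI, waist circumference", then "Fasting glucose and insulin with calculation of the" QUICKI index, then HbA1c and the fasting lipid panel.

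Section 6.16 covers diabetes that appears during the study. The participant may continue, and "in the event a participant is found to have diabetes on follow up metabolic testing, their primary care provider will be notified". It does not mention the adverse-event log.

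Section 8 lists anorexia as an adverse event, with the remark "Loss of appetite is one of the mechanisms contributing to weight loss". It does not list weight loss itself.

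**The concern.** The exception is sensible for efficacy instruments: nobody wants each fall in IENFD or rise in NQOL-DN entered as an adverse event. But its wording reaches every outcome measure, and several secondary outcomes here are also safety variables for this drug. Section 2.4 expects topiramate to lower weight and alter insulin sensitivity. A site that follows the text would leave off the log a weight loss, or an isolated HbA1c, glucose or lipid value, that the investigator considers clinically significant and harmful. A site that follows the laboratory rules would log it. What is at stake is consistent safety capture: the medical monitor's review (10.2) and the quarterly, MedDRA-coded reports (11.4) are built from recorded adverse events.

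**Working it through.** The plan gives no figure on this point and no arithmetic applies. The check sets the provisions side by side.

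1. **Scope of the exception.** Section 11.4.1.1 states it twice and names no instrument either time. Section 10.1.2 uses the same term, outcome measures, and places metabolic assessment under it. Nothing in 11.4.1.1 gives the term a narrower meaning.

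2. **What each rule does to each finding.**

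| Finding | Under the exception | Under other text |
|---|---|---|
| Weight, BMI | Barred (outcomes in 10.1.2) | Appendix A puts both in the vital-signs row, and 11.4.1.1 counts clinically significant vital signs |
| Waist circumference | Barred | No specific rule |
| Fasting glucose | Barred | 7.1.12 lists glucose in the basic metabolic panel as safety monitoring; significance is judged by the investigator |
| Fasting insulin, HbA1c, lipids | Barred | 7.1.12 has out-of-range values judged for significance; 11.4.1.1 has a significant anomaly that is not part of a disease logged as its own event |
| 2-hour OGTT glucose | Not barred (absent from 10.1.2) | Recordable |
| New diabetes, as a diagnosis | Not barred (the exception covers results) | 11.4.1.1 counts new conditions and has the disease itself logged |

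3. **The contradictions that follow.** An HbA1c or triglyceride value marked clinically significant under 7.1.12 falls under two opposite instructions within 11.4.1.1. Appendix A, footnote 4, says that the fasting glucose is the pre-dextrose sample of the OGTT, so two values from one test fall under opposite rules. For weight the conflict rests on Appendix A alone, because 7.1.6 defines vital signs as blood pressure, heart rate and temperature. If 7.1.6 governs, measured weight loss has no competing rule and is simply barred.

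4. **New diabetes.** Section 11.4.1.1 exempts diabetes only when it predates the study and has not worsened. Anyone with diabetes at screening is excluded (4.2), so a case arising on study is a new condition and belongs on the log. Section 6.16 is silent on this; it does not say the opposite.

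5. **Where a barred result still goes.** By 11.4.1.1 it is collected and analysed separately. Section 10, under secondary outcomes, gives between-arm models for continuous secondary outcomes. Section 10.2 has the DSMB monitor endpoints as well as adverse-event rates. A barred result does not reach the medical monitor's adverse-event review, the event tables or MedDRA coding.

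**The case against.** The strongest reply is that this is a drafting matter with little consequence. An adverse event must be unfavourable and not intended. In a population with BMI of at least 25 and metabolic syndrome, weight loss is a proposed mechanism of benefit, so most of it would not qualify under any wording. Loss of appetite, and any complaint or examination sign, is still captured by the clinical route in 11.4.1.1. Differences between arms in weight and metabolic values will be estimated directly. All of this stands, and it limits the harm. It does not remove the problem, because an arm-level mean is no substitute for review of an individual finding that the investigator judged clinically significant.

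A reader might infer more than the documents support:

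- *New diabetes is never reported.* It is recordable as a new condition, as shown under the working.
- *The number of missed events can be projected from the weight-loss figures in 2.4* (6.6% over 11 months in obese diabetic patients; 7.3% at one year in epilepsy, 11% in those with BMI of 30 or more). Those are means without a spread, from other populations. A large loss is also not in itself an adverse event. The documents give no rate of clinically significant, unfavourable weight loss.
- *The arms are under-counted unequally.* Because the drug is expected to shift these variables, this is possible, but nothing in the documents demonstrates it.
- *The decision on a full-scale trial is distorted.* The Go/No-Go rule in section 10 uses only IENFD and NQOL-DN.
- *The withdrawal lists contradict the exception.* Sections 4.3 and 6.13 give "Major/clinically significant alteration in laboratory values after beginning study drug" under an adverse-event heading, but a bicarbonate, creatinine or blood-count result would satisfy that without being an outcome measure.

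**Conclusion.** The concern holds in a limited form. As written, 11.4.1.1 bars recording a clinically significant measured change in weight, BMI, waist, fasting glucose, fasting insulin, HbA1c or fasting lipids as an adverse event. For the laboratory values this contradicts the laboratory-anomaly rule in the same section and the significance judgement in 7.1.12. For weight it contradicts the Appendix A grouping. Such findings would bypass medical-monitor review and the coded event tables. They would not be lost to the between-arm analysis or to the DSMB.

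The number of findings affected cannot be derived from the documents. No sample size, power, error rate or efficacy analysis changes. The conclusion assumes that outcome measures means in 11.4.1.1 what it means in 10.1.2, and that no separate site guidance narrows the exception; the documents show none.

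**What to change.** In 11.4.1.1, at both places where the exception appears, restrict it to named efficacy instruments: IENFD, NQOL-DN, NTSS-6, BPI-DN, UENS, 6MWT, TUG, the ABC scale and nerve conduction studies. Add that a weight or metabolic result which the investigator judges both clinically significant and unfavourable is recorded as an adverse event. The second condition keeps expected, beneficial weight loss off the log. In 6.16, add that diabetes diagnosed during the study is logged as a new condition under 11.4.1.1. Carry the same wording into any adverse-event guidance for sites.

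The cost is a few sentences and slightly more adverse-event entries. No new test or visit is needed, and the statistical analysis does not change.
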